**Table 7. Response Criteria**

Target lesions	Non-Target lesions	Overall response
CR	CR	CR
CR	Incomplete response/SD	PR
PR	Non-PD	PR
MR	Non-PD	MR
SD	Non-PD	SD
PD	Any	PD
Any	PD	PD
Any	Any	PD

Patients with a global deterioration of health status requiring discontinuation of treatment without objective evidence of disease progression at that time should be classified as having "symptomatic deterioration". Every effort should be made to document the objective progression even after discontinuation of treatment. In some circumstances it may be difficult to distinguish residual disease from normal tissue. When the evaluation of complete response depends on this determination, it is recommended that the residual lesion be investigated (fine needle aspirate/biopsy) to confirm the complete response status.

### **10.4 Confirmation**

The main goal of confirmation of objective response is to avoid overestimating the response rate observed. To be assigned a status of PR or CR, changes in tumor measurements must be confirmed by repeat assessments that should be performed no less than 4 weeks after the criteria for response are first met. In the case of SD, follow-up measurements must have met the SD criteria at least once after study entry at a minimum interval (in general, not less than 6-8 weeks) that is defined in the study protocol.

### **10.5 Duration of overall response**

The duration of overall response is measured from the time measurement criteria are first met (i.e., not from time of confirmation of response) for CR or PR (whichever status is recorded first) until the first date that recurrence or PD is objectively documented, taking as reference for PD the smallest measurements recorded since the treatment started.

### **10.6 Duration of stable disease**

SD is measured from the date of first protocol treatment until the criteria for disease progression are met, taking as reference the smallest measurements recorded since the treatment started.

### **10.7 Time to Progression**

The time to progression (TTP) is defined as the time from the date of first protocol treatment until the date disease progression criteria are met (in responding patients progression criteria uses the reference of the smallest measurements recorded since the treatment started) or is censored at date of last disease assessment for those who have not progressed.

### **10.8 Progression-free Survival**

Progression-free survival (PFS) is defined as the time from date of first protocol treatment until the date disease progression criteria are met (in responding patients progression criteria uses the reference of the smallest measurements recorded since the treatment started) or date of death from any cause, or is censored at date of last disease assessment for those who have not progressed.

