### **Agents**

- **Hydroxychloroquine** oral at 600 mg/d throughout the treatment. Continuous oral administration will be initiated prior to the first dose (day -14), given a minimum of 14 days (maximum of 21 days) prior to initiation of the first dose of IL-2 and then daily or twice a day throughout all three treatment courses.
- **Aldesleukin (IL-2)** 600,000 IU/kg IV bolus q 8 hrs beginning on day 1 and day 15 (maximum 14 doses per cycle).

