## 5.0 PRE-STUDY TESTING/STAGING

All patients considered for entry in the trial should have measurable or evaluable metastatic disease as described in the RECIST 1.1 criteria (see Section 11.0). Staging will include:

- 5.1 History and physical examination within two weeks of the first day of treatment (day -14).
- 5.2 Within 4 weeks prior to treatment (day -14), the following procedures are required:
  - 5.2.i CT scans of the chest/abdomen/pelvis
  - 5.2.ii Brain MRI or enhanced brain CT
  - 5.2.iii Bone scan (if clinically indicated)
  - 5.2.iv Cardiac stress test: All patients over 40 years of age or with significant cardiac history
  - 5.2.v Pulmonary function tests within 4 weeks of starting therapy for all patients over 50 years old or with significant pulmonary or smoking history
  - 5.2.vi Cardiac ECHO or MUGA scan to assess LVEF
  - 5.2.vii 12-lead EKG
- 5.3 Within 2 weeks prior to treatment (day -14) the following procedures are required:
  - 5.3.i Urine protein:creatinine ratio (see appendix A)
  - 5.3.ii Urinalysis
  - 5.3.iii Laboratory tests: HIV, hepatitis B and C serology, pregnancy test when indicated, CBC with differential, comprehensive metabolic panel (creatinine, BUN, albumin, total protein, glucose, electrolytes, liver function tests [total bilirubin, alkaline phosphatase, aspartate aminotransferase, alanine aminotransferase]), direct bilirubin, LDH, Ca, PO4, TSH, PT, PTT. A serum sample for determination of serum VEGF/ANG1/ANG2 levels will be drawn on day -14, prior to the dose of hydroxychloroquine.
- 5.4 Within 4 weeks after enrollment, tissue blocks or four unstained slides of renal tissue sent to central pathology facility.

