### **6.4 Response Assessment/ Duration of Therapy**

Patients will undergo CT scans at week 8 and week 12 (+/- 1 week) following initiation of IL-2 therapy and then after each course (every 10-12 weeks). After the final course (week 36), patients will undergo CT scan evaluation every 12 weeks (+/- 2 weeks) for up to one year or until tumor progression (whichever comes first). If additional scans are performed for clinical reasons, the study schedule may be altered to perform the requisite scans at a more acceptable time point. The change in timing of study scans must be approved by the local PI and documented. For patients who have not shown progression at the end of one year, response will be captured during follow-up for survival (explained below).

Patients with evidence of tumor shrinkage with all lesions measurable and evaluable may receive up to 3 courses of IL-2 therapy. Course 2 will start on or within 2 weeks following day 85 and follow the same schedule as in Course 1. Course 3 can start within 2 weeks of completion of Course 2. Patients not receiving IL-2 during course 2 with tumor shrinkage by week 24 can receive a 2nd course of IL-2 beginning within 2 weeks of week 25.

Patients with no evidence of progression by RECIST 1.1 criteria may receive continued treatment with hydroxychloroquine through one year of initiation of HCQ treatment (Day -14) or until disease progression.

Tumor response will be assessed by the NCI’s Response Evaluation Criteria in Solid Tumors (RECIST) 1.1 guidelines. Patients will undergo tumor evaluation with physical exam and CT scans at week 8 (+/- 1 week) and week 12 (+/- 1 week), then after each course (every 10-12 weeks). After the final course (week 36), patients will undergo CT scan evaluation every 12 weeks (+/- 2 weeks) for up to one year or until tumor progression (whichever occurs first). If additional scans are performed for clinical reasons, the study schedule may be altered to perform the requisite scans at a more acceptable time point. The change in timing of study scans must be approved by the local PI and documented. For patients who have not shown progression at the end of one year, response will be captured during follow-up for survival, which will be done on all patients via telephone contact and medical record review. Patients with progressive disease by RECIST 1.1 criteria will be taken off study.

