### **10.9 Survival:**

Survival is calculated from the date of first protocol treatment to the date of death, or censored at date of last contact.

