### 13.2 Analysis Plan

The data will be analyzed for response, overall survival and other endpoints, as described in this section; data will only be analyzed as specified in Section 14.3.1 to ensure the toxicity of IL-2+HCQ is not unexpectedly high. All analyses will be performed using the most recent versions of SAS and/or R available.

- 13.2.1.** *Estimate the proportion of patients with metastatic RCC treated with IL-2 combined with hydroxychloroquine at 600mg/d who experience a clinical complete response.* Response is defined in Section 10.3. The probability of each category of response will be estimated. Secondary analyses will employ cumulative logit regression for increasing levels of response, with adjustment for demographic and clinical covariates. All point estimates will be accompanied by appropriate 95% confidence intervals.
- 13.2.2.** *Compare the response, overall survival and time to progression of patients with metastatic RCC treated with IL-2 combined with hydroxychloroquine to the published response of patients treated with high dose IL-2 alone.* Logistic and proportional hazards (Cox) regression will be used to compare clinical response, and OS and PFS, respectively, to examine the effect of HCQ on the efficacy of IL-2. Formal tests of non-inferiority are beyond the scope of this Phase II study, and these secondary analyses are not statistically powered.
- 13.2.3.** *Characterize the toxicity of IL-2 combined with hydroxychloroquine in patients with metastatic RCC: number of doses of IL-2 administered during the first course of therapy; toxicity after the scheduled 9th dose of IL-2; frequency of grade III and IV or unexpected or rare toxicities.* Number of doses, maximal toxicity grade and incidence of treatment-limiting toxicities (TLTs, as defined in Section 10.5) will be tabulated.

**13.2.4** *Evaluate the utility of known prognostic criteria for RCC patients on clinical outcome.* Prognosis is evaluated by whether the patient has 0, 1, or 2, or 3 or more of the following risk factors:

- lactate dehydrogenase (> 1.5 upper limit of normal)
- hemoglobin (< lower limit of normal)
- corrected calcium (>10mg/dL)
- Karnofsky performance status (< 80%)
- time from initial RCC diagnosis to start of interferon- $\alpha$  therapy of less than one year

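### PFS and OS appear to run from the start of HCQ, and Section 13.2.2 compares them with IL-2-alone data whose time origin is neither stated nor aligned

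*Combined protocol and SAP*

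**What the plan says.** Section 10 gives all three time-to-event endpoints the same origin. PFS: "Progression-free survival (PFS) is defined as the time from date of first protocol treatment until the date disease progression criteria are met". TTP "is defined as the time from the date of first protocol treatment until the date disease progression criteria are met". OS: "Survival is calculated from the date of first protocol treatment to the date of death". Section 10 does not say which of the two drugs this refers to.

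Other sections do date the start of treatment. Section 5.1 asks for a history and examination "within two weeks of the first day of treatment (day -14"), and Section 5.2 says: "Within 4 weeks prior to treatment (day -14), the following procedures are required". Section 6.4 links the initiation of HCQ to day -14, and Appendix B heads that day as the study start. The Agents part of the Summary has HCQ "given a minimum of 14 days (maximum of 21 days) prior to initiation of the first dose of IL-2".

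The scans have a different anchor. Section 6.4: "Patients will undergo CT scans at week 8 and week 12 (+/- 1 week) following initiation of IL-2 therapy".

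Section 13.2.2 then plans the historical comparison: "Logistic and proportional hazards (Cox) regression will be used to compare clinical response, and OS and PFS, respectively". It describes this as secondary and not powered. The comparator is the Proclaim database and publication in Section 1.2. Section 2.2 offers the Select trial for comparison, and Sections 2.17 and 6.1 describe a historical group matched on prognostic factors. No section gives a time origin or scan schedule for any of them.

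**The concern.** The HCQ lead-in exists in the trial cohort only. If trial time is counted from HCQ and comparator time from the first IL-2 dose, the trial patients carry two to three extra weeks that have nothing to do with efficacy. Because scans are counted from IL-2, a progression found at the week 8 scan is recorded at week 10 or 11.

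This is not trivial against short PFS. The documents give IL-2-alone medians of 3 months (Section 2.3) and 4.3 months (Section 2.2), and Section 2.2 notes that about half of patients in prior studies progressed at the first scan. Section 13.2.2 is meant to show the effect of adding HCQ, so a clock difference tied to HCQ cannot be told apart from the effect sought. Leaving the origin open also allows it to be chosen after the data are seen.

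**Working it through.** **The plan's own figure.** Section 13.4 gives an expected width of 12.8 months for the 95% CI of median survival (39 patients, 15 months' accrual, 15 months' further follow-up, median 16 months). With λ = ln 2/16 = 0.0433, expected events are 39 × [1 − (e^(−15λ) − e^(−30λ))/(15λ)] = 24.03. The width is 2 × 1.96 × 16/√24.03 = 12.8 months. It reproduces, and it does not depend on which drug starts the clock.

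**Size of the clock difference.** One month is 365.25/12 = 30.44 days.
- 14/30.44 = 0.46 months; 21/30.44 = 0.69 months.
- Against a median PFS of 4.3 months: 0.46/4.3 = 11%, 0.69/4.3 = 16%.
- Against a median PFS of 3 months: 0.46/3 = 15%, 0.69/3 = 23%.

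The median rises by this full amount only if nobody progresses during the lead-in. With continuous times and the hazard running from HCQ start, the gain is 0. Lead-in progression is possible, since the baseline CT may be up to four weeks before day -14.

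**Null hazard ratios, HCQ origin.** Let T be the time to progression, with the same distribution in both cohorts (no HCQ effect), and L the lead-in. The comparator records T from IL-2. The trial records T + L if the hazard starts at IL-2, and T if it starts at HCQ. For scan-detected times, T is replaced by the first scan at or after it, timed from IL-2, plus L in the trial.

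Assumptions: comparator clock at IL-2; same scan schedule in both cohorts (weeks 8, 12, 24, 36, then every 12 weeks, each ±1 week); weighting 39:123 (123 is the Select trial's size; none is given for Proclaim); cut-off 24 months; Efron ties; 150,000 simulated patients per cohort. The front-loaded curve has 50% progression-free at week 8 and 11% at 36 months. Pairs are for L = 14 / 21 days.

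| PFS curve | Hazard from IL-2, continuous | Hazard from IL-2, scan-detected | Hazard from HCQ, continuous | Hazard from HCQ, scan-detected |
|---|---|---|---|---|
| Exponential, median 3.0 mo | 0.90 / 0.86 | 0.78 / 0.78 | 1.00 / 1.00 | 0.84 / 0.86 |
| Exponential, median 4.3 mo | 0.93 / 0.89 | 0.84 / 0.83 | 1.00 / 1.00 | 0.88 / 0.90 |
| Front-loaded | 0.90 / 0.86 | 0.80 / 0.79 | 1.00 / 1.00 | 0.81 / 0.81 |

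The scan-detected values mainly reflect the order of clustered scan dates, not the length of delay. With the hazard from IL-2 they are 0.97 for a 1-day lead-in, 0.83–0.87 for 7 days and 0.78–0.83 for 14 days, and change little by 21 days. If scans follow Appendix B footnote b (weeks 8 and 12 of each course), the range with the hazard from IL-2 is 0.81–0.87.

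**Other comparator assumptions.**
- Comparator clock starting 14 days before IL-2, with a 14-day lead-in: 1.00.
- Comparator first scanned at week 12, exponential curves: 0.87–0.90 (hazard from IL-2) and 0.97–1.01 (hazard from HCQ). With front-loaded curves (50% progression-free at week 8 or week 12): 1.03–1.24.
- Trial counted from IL-2, nobody excluded, same scans: 1.00 without lead-in progression. With the hazard from HCQ it is 1.08–1.17 continuous and 1.03–1.14 scan-detected. The IL-2 origin is therefore not automatically neutral either.

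**OS** (medians 16, 17 and 42.8 months, cut-off 30 months, HCQ origin): 0.96–0.98 without lead-in deaths, 1.00 with the hazard from HCQ.

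**Against sampling error.** Assuming 35 and 115 events, the SE of the log hazard ratio is √(1/35 + 1/115) = 0.193. An HR of 0.84 then has a 95% CI of 0.84 × e^(±1.96 × 0.193) = 0.58 to 1.23.

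**The case against.** The strongest reply is that the trial's origin can be found. Sections 5 and 6.4 and Appendix B all put the start of treatment at day -14, and HCQ is part of the regimen. That stands: a reader might infer from Section 10 alone that the origin is undefined, and the documents as a whole do not support this. What is missing in Section 10 is an explicit statement. The HCQ reading does not settle the comparison, however. It makes the gap concrete, because the scans and the comparator treatment are both tied to IL-2.

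The second reply is that the harm depends on facts outside the documents. This also stands. A reader might infer that the comparison is biased in favour of HCQ. The documents do not support that, because they give no comparator origin or scan schedule, and the null hazard ratios above run from 0.78 to 1.24 across plausible choices.

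Third, the comparison is secondary and unpowered, and a historical comparison of this size has wide uncertainty anyway. That limits the severity. It does not justify leaving the clocks unaligned, because a wide interval does not remove a shift in the estimate.

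Finally, first protocol treatment is a reasonable origin for a regimen with a lead-in, and restricting to IL-2 starters drops patients who fail before IL-2. Both are true, which is why both origins and the lead-in losses should be shown.

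**Conclusion.** The point holds as a low-severity gap in the analysis plan. As written, the plan most naturally counts PFS and OS from HCQ start, 14 to 21 days before IL-2, and compares them with IL-2-alone data whose clock is not stated or aligned.

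If the comparator is dated from IL-2 and scanned on the same schedule, the null PFS hazard ratio with no lead-in progression is about 0.86–0.93 with continuous times and about 0.8 to 0.85 when scan-detected. With the hazard starting at HCQ it is 1.00 and about 0.8 to 0.9. Both conditions are assumptions; changing either can remove or reverse the effect. OS changes little (0.96–1.00 from the HCQ origin), and the primary complete-response estimate is not affected.

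**What to change.** In 10.7–10.9, state that first protocol treatment is the first HCQ dose, if that is intended. In 13.2.2:
- Name the comparator and give its documented time origin and scan schedule.
- Run the PFS and OS comparison from the matching trial origin (first IL-2 dose, if the comparator is dated from IL-2), with the HCQ-start origin reported alongside. If the comparator's origin is undocumented, report both with equal standing.
- Report deaths, progressions and dropouts during the HCQ lead-in, because an analysis of IL-2 starters omits them.

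The cost is one definition, a short paragraph and a check of the comparator's methods. No new trial data are needed. PFS against the benchmark may look slightly less favourable, and some uncertainty remains because a published comparator's origin and scan schedule cannot be reset.

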### **10.9 Survival:**

Survival is calculated from the date of first protocol treatment to the date of death, or censored at date of last contact.

## 11.0 PARTICIPANTS EVALUABLE FOR RESPONSE

Reporting of results:

Clinical Results: All patients included in the study will be assessed for response to treatment, even if there are major protocol treatment deviations or if they are ineligible. Each patient will be assigned one of the following categories:

- 1) complete response
- 2) >90% partial response
- 3) partial response
- 4) stable disease
- 5) progressive disease
- 6) early death from malignant disease (within 3 months of initiating therapy)
- 7) early death from toxicity
- 8) early death because of other cause
- 8) unknown (not assessable, insufficient data).

All patients who met the eligibility criteria and receive at least one week of IL-2 treatment will be included in the main analysis of the response rate. Patients in response categories 5-8 will be considered as failing to respond to treatment (disease progression). Thus, an incorrect treatment schedule or drug administration does not result in exclusion from the analysis of the response rate.

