### 1.1 Primary:

1. Estimate the proportion of patients with metastatic RCC treated with IL-2 combined with hydroxychloroquine at 600 mg/d who experience a clinical complete response.

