### 4.4 Cancellation Guidelines

No patient will be cancelled. Data will be collected on all patients, even if a patient does not receive protocol therapy. Reasons for a patient not initiating therapy should be submitted in writing as soon as possible. All patients receiving at least one week of IL-2 treatment and two weeks of oral HCQ will be included in the final evaluation.

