## 13.0 STATISTICAL ANALYSIS AND STUDY SIZE

### 13.1 Objectives and Design

The primary objective of this Phase II trial is to estimate the proportions of patients with metastatic RCC treated with high-dose IL-2 combined with hydroxychloroquine experiencing complete response, or any response. The secondary objectives are to compare response, time to progression and survival to historical data to determine the toxicity of the treatment regimen, to evaluate PD, and to examine correlative science endpoints. Disease endpoints are defined in Section 10.

The accrual goal is 39 participants. All study participants will receive the same high-dose IL-2 treatment, which is considered standard of care. The initial dose of HCQ will be 600 mg/day for all patients. If no limitations on additional dosing (treatment-limiting toxicities [TLTs], as defined in Section 9.2), dosing will continue at 600mg/d, otherwise, HCQ will de-escalate to 400 mg/d. Toxicity and response will be monitored after every three patients (Section 13.4), and will be stopped if the probability that treatment with IL-2+HCQ is excessively toxic or ineffective. The study may be opened more broadly to additional Cytokine Working Group sites whenever sufficient evidence has accrued that treatment with IL-2+HCQ is no more toxic or less effective than treatment with IL-2 alone.

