### 13.4 Justification of Design

The primary objective of this study is to estimate the clinical response rate of patients with metastatic RCC treated with IL-2 combined with hydroxychloroquine at 600mg/d. Assuming no TLTs occur and the trial is not closed early for toxicity or inadequate response (Section 13.3.2), there will be 39 patients available for this objective. A 95% exact binomial confidence interval on 5 responses out of 39 patients (expected if the addition of HCQ to IL-2 doubles the historic proportions of CR ~ 8%) would have width equal to 0.27 (0.07,0.34). For the secondary endpoints of OS and PFS, if patients are recruited over 15 months, observed for 15 additional months, and the true median survival is 16 months, then the expected width of the 95% confidence interval for median survival is 12.8 months.

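### Section 11.0 makes entry to the main response analysis depend on eligibility and an undefined week of IL-2, against its own all-patient statements, 4.4's different set and 13.4's count of 39

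*Combined protocol and SAP*

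**What the plan says.** The primary objective (1.1) is to "Estimate the proportion of patients with metastatic RCC treated with IL-2 combined with hydroxychloroquine at 600 mg/d who experience a clinical complete response". Four places bear on who is in the denominator.

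- **11.0** opens by requiring that every patient be assessed for response, including ineligible patients and those with major treatment deviations. Each is assigned a category; the list includes early death from disease, from toxicity or from other causes, and unknown. For the response rate it then narrows: "All patients who met the eligibility criteria and receive at least one week of IL-2 treatment will be included in the main analysis". Categories 5 to 8 count as failures. It ends by saying that a wrong schedule or wrong drug administration is not a reason for exclusion.
- **4.4** states: "All patients receiving at least one week of IL-2 treatment and two weeks of oral HCQ will be included in the final evaluation". It has no eligibility condition. It also states: "Data will be collected on all patients, even if a patient does not receive protocol therapy".
- **13.2.1** plans the primary analysis ("The probability of each category of response will be estimated") but names no analysis set.
- **13.1 and 13.4**: "The accrual goal is 39 participants", and, provided there are no treatment-limiting toxicities and no early closure, "there will be 39 patients available for this objective".

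On timing, 5.1 to 5.3 place the first day of treatment at day -14. The Summary (Agents) gives HCQ for 14 to 21 days before the first IL-2 dose. Section 6.2 gives IL-2 on days 1-5 (or 6) and 15-19 (or 20), and 9.2 says missed IL-2 doses are not made up.

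**The concern.** The primary result is a single-arm proportion, so the choice of denominator directly determines the estimate. Here membership depends on treatment received after enrolment and on a threshold with no definition in days or doses. A patient stopped on day 2 of cycle 1 is in or out depending on the reader, and that choice could be made once responses are known.

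The rule also works against the rest of 11.0. Early toxic deaths are meant to count as failures, yet a patient who dies in the first days of IL-2 may never enter the analysis. A patient who starts HCQ and progresses, withdraws or dies before IL-2 is outside the main response analysis. The same patient's progression-free and overall survival clocks have already started, because 10.8 and 10.9 count from first protocol treatment. This last point follows from the wording; the protocol does not state it outright.

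**Working it through.** **1. The rules side by side**

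| Condition | 11.0, opening | 11.0, main analysis | 4.4, final evaluation | 13.4 |
|---|---|---|---|---|
| Must be eligible | No | Yes | Not stated | Not stated |
| IL-2 needed | None | One week | One week | Not stated |
| HCQ needed | None | None | Two weeks | Not stated |
| Number | All | Not given | Not given | 39 |

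The real difference between 11.0's main analysis and 4.4 is eligibility. The two-week HCQ condition adds little, because the lead-in is already at least 14 days.

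**2. What one week could mean.** A cycle gives IL-2 on 5 or 6 days.
- Seven consecutive dosing days never occur within a cycle, so that reading empties the set.
- Seven dosing days in total are reached only in the second cycle (5 + 2 or 6 + 1), which drops everyone who stops after cycle 1.
- A completed first cycle drops early stoppers.
- Having entered the first treatment week keeps them.

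**3. The plan's own figure.** Section 13.4 describes "A 95% exact binomial confidence interval on 5 responses out of 39 patients" and prints (0.07, 0.34), width 0.27. The exact (Clopper-Pearson) limits are the beta quantiles B(0.025; x, n-x+1) and B(0.975; x+1, n-x). With x = 5 and n = 39 they are 0.043 and 0.274, width 0.231. The printed interval does not reproduce. That is a separate matter; the recomputed interval is used below.

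**4. Effect of exclusions.** If d excluded patients cannot have a CR, the rate is multiplied by 39/(39 - d).

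| d (assumed) | Multiplier | CR rate | Exact 95% CI |
|---|---|---|---|
| 0 | 1.000 | 5/39 = 12.8% | 4.3 to 27.4 |
| 1 | 1.026 | 5/38 = 13.2% | 4.4 to 28.1 |
| 2 | 1.054 | 5/37 = 13.5% | 4.5 to 28.8 |
| 4 | 1.114 | 5/35 = 14.3% | 4.8 to 30.3 |

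The shift is 0.3 to 1.5 percentage points, against an interval about 23 points wide. The upward direction is certain only for patients who cannot have a CR, such as those who never received IL-2 or died before assessment. For ineligible patients, or those who stopped after a few IL-2 doses, it could go either way.

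**5. How large d might be.** The documents give no exclusion rate for this trial. Section 2.3 offers a rough scale from the phase III comparison of high-dose IL-2 with IL-2/interferon, which had no HCQ lead-in:
- 193 enrolled and 192 evaluable: 1/193 = 0.5%, and 0.005 × 39 = 0.2 patients.
- Response denominators 95 + 91 = 186, so 193 - 186 = 7: 7/193 = 3.6%, and 0.036 × 39 = 1.4 patients.

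Four exclusions therefore lie beyond both figures and serve only as an upper illustration.

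**6. The 39 itself.** Section 2.18 gives 5 earlier patients at 600 mg/d, 13 at 1200 mg and 21 more to be accrued: 5 + 13 + 21 = 39. The objective is worded for 600 mg/d, and 5 + 21 = 26. If the denominator is 26, each exclusion counts for more: for illustration, 4/26 = 15.4% and 4/24 = 16.7%.

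**The case against.** The strongest reply is that 11.0 already requires a response category for every patient, including ineligible patients and early deaths, and 13.2.1 estimates every category. On that view only a label is missing. Its closing sentence, and the counting of categories 5 to 8 as failures, also favour the reading that keeps early stoppers. This is fair: the data will exist, and the text leans towards inclusion. It does not settle the point, because the sentence that defines the main analysis still imposes both conditions and 13.2.1 does not say which set is primary.

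It can also be said that 4.4 does not mention the response rate, so its conflict with 11.0 is thin. That stands in part: 4.4 does not call itself the primary set, but a final evaluation with different membership still needs reconciling.

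Third, objective 1.1 concerns patients treated with both drugs, so leaving out those who received only HCQ is defensible. This stands, and the fix respects it. The objective does not, however, supply a one-week threshold or an eligibility filter.

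A reader might go further and infer that the Table 8 futility rule is materially compromised, since 13.3.2 counts patients who become evaluable for response. The documents do not support that. They do not say which set this means, and the prior (8/95) comes from patients given high-dose IL-2, so adding patients who never received IL-2 would put a different population into the rule. Any missed halt also depends on assumed dropout: at 0.5%, simulation gives 0.2 to 0.4% of trials at true response rates of 5 to 10%.

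**Conclusion.** The concern holds as a conflict in the definition of the primary denominator. Section 11.0's main-analysis rule contradicts its own all-patient statements, differs from 4.4, and is ignored by 13.4. Followed as written, it removes lead-in dropouts and, on a literal reading, can remove early cycle-1 stoppers and deaths. Where those patients cannot have a CR, the reported rate can only rise.

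The expected size is small: 0.3 to 1.5 points on 5/39 for 1 to 4 exclusions, and zero if nobody is excluded. This rests on an assumed number of exclusions, on 13.4's example of five responses, and on a denominator of 39 that may not be the 600 mg/d group. The reason to act is that the rule leaves the primary denominator open to choice after the results are seen, and closing it costs little. It would be wrong to conclude that the CR estimate is seriously biased or that the futility monitoring fails.

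**What to change.** - In 11.0 and 4.4, name one primary response set with no one-week threshold and no exclusion for ineligibility found later: all enrolled patients who received at least one dose of IL-2 with HCQ. Count anyone without a documented CR, including early deaths and unknowns, as not CR.
- Report two labelled sensitivity analyses: (i) all patients who started any protocol treatment, with HCQ lead-in dropouts as non-responders; (ii) the existing one-week set, with the week defined in doses or days.
- Cite the primary set in 13.2.1, and state in 13.3.2 which set is meant by evaluable for response.
- Reconcile the 39 in 13.4 with the number at 600 mg/d (26 by the counts in 2.18).

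The cost is wording in 4.4, 11.0, 13.2.1, 13.3.2 and 13.4. No new data are needed, because 4.4 already collects data on all patients. The downside is a slightly lower reported CR rate than the one-week set might give.
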